For this modification, the only *major* changes to the protocol included the recruitment incentive and increase in the upper patient age limit, which our funder, PCORI, had already suggested and verbally approved in March 2018. Thus, at that time, we submitted the following 2nd (and minor) revision of our study protocol to the UMass IRB, which was approved in March

2018. This was the final protocol in place for the remainder, and majority, of the study. (Note that the protocol still references the diagnostic interviewing component, as that study element was not jettisoned until September 2018, as per the contract modification details noted above.)

**PROTOCOL
APPLICATION FORM
SOCIAL, BEHAVIORAL, AND EDUCATIONAL FULL BOARD
HUMAN SUBJECTS IN SOCIAL, BEHAVIORAL, AND EDUCATIONAL
RESEARCH**

**University of Massachusetts Amherst (UMass)
Institutional Review Board (IRB)**

Protocol ID: 2016-3401

Title: Enhancing Mental Health Care

Revision Form

1. Summarize the proposed changes to the protocol in lay terms (including details of ALL changes proposed AND modify all relevant protocol sections and attachments accordingly).

By way of a brief reminder, subjects in the current study include two mental health care stakeholder groups: (1) therapists affiliated with Psychological and Behavioral Health Consultants (PsycBC) who are providing outpatient psychotherapy, and (2) adult patients receiving psychotherapy (for varied mental health complaints) from the participating PsycBC therapists. PsycBC is a formal subcontract to UMass on this project, and their role on this project is restricted to providing the research team access to these two subject populations, and assisting the team in recruitment. Thus, PsycBC is not engaged in human subjects' research. The amendment proposed here deals solely with patient recruitment procedures. There are no changes to the research protocol itself.

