For the primary 3-level hierarchical model assessing treatment condition effects at the patient level on linear change rates within patients, we used Raudenbush and Liu's (2001) formula as incorporated in the Optimal Design program to determine the minimum numbers of therapists and patients needed to detect a moderate effect of condition (standardized difference between change rates = .50). With a minimum of 6 measurements spaced over the maximum 16 treatment weeks and assuming 5 patients per therapist, an intra-class correlation of .15, and an alpha of .05, we will need a total of 44 therapists and 220 patients to achieve a power of .80 to detect moderate condition effects on linear change rates. Factoring a 20% dropout rate at the patient level, running our experiment on 264 patients (6 per therapist) should provide sufficient statistical power to detect group differences on our primary outcome variables.

To summarize, based on this power analysis, we will for phase 1 access a naturalistic baseline assessment of a minimum of 44 consenting therapists' performance across a minimum of 15 cases to determine their strengths in treating the risk-adjusted domains measured by the TOP. We will then recruit a minimum of 264 patients for the phase 2 trial, assigning patients to the same 44 therapists who participated in phase 1 (they will see 6 cases each during the trial).

b. Describe the subject population, including the age range, gender, ethnic background, and type of subjects (e.g. students, professors, subjects with learning disabilities, mental health disorders, etc.). Please incorporate specific inclusion/exclusion criteria (e.g. physical and psychological health, demographic information, or other unique characteristics).

Therapist participants: As noted, our target sample is 44 therapist participants (age range = 30-65 years) who will be social workers, psychologists, and licensed clinical counselors. Reflecting PsycBC's therapist pool demographics, we anticipate that our provider sample will break down as follows: approximately 70% will be female; 88% will be white/non-Hispanic, 3% Black, 2% Hispanic, 2% "Other/mixed," and 5% Asian. Based on these projections and our power analysis, our targeted/planned therapist enrollment is indicated in an attached Targeted/Planned Enrollment Table (Therapists).

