- We updated our patient enrollment target from 264 to 281 based on a more conservative attrition rate of 25% (up from our original, less conservative estimate of 20%). With this modification, enrolling 281 patients into the trial allowed us to meet our target of 211 usable case for final data analysis ($281 * .75 = 211$). Based on this adjustment, we also updated accordingly our *Estimated Final Racial/Ethnic and Gender Enrollment Table*.
- We updated our timeline and milestone schedule based on the PCORI-approved 6-month extension to the contract end date. This no-cost extension was precipitated by delays in patient recruitment, which we successfully addressed via our formal project remediation plan.

For this modification, there were no changes to the study protocol.

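### The dropout allowance in section 4a leaves about 211 patients, not the 220 stated as needed for .80 power; the later 281 target is sized to 211 and power is not restated

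*Combined protocol and SAP*

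**What the plan says.** Section 4a (Subject Population, number of subjects and rationale) of the 2nd revision bases the sample size on a three-level growth model. The effect to detect is given as "standardized difference between change rates = .50", with the further inputs "assuming 5 patients per therapist, an intra-class correlation of .15, and an alpha of .05". The result is "we will need a total of 44 therapists and 220 patients to achieve a power of .80", and these are described as minimum numbers. The next sentence makes the allowance for attrition: "Factoring a 20% dropout rate at the patient level, running our experiment on 264 patients (6 per therapist) should provide sufficient statistical power". The same figures appear in section 4a of the initial protocol and of the 1st revision.

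Part D, the summary of the 3rd contract modification, changes the enrolment target from 264 to 281, "based on a more conservative attrition rate of 25% (up from our original, less conservative estimate of 20%)". It gives the reason that "enrolling 281 patients into the trial allowed us to meet our target of 211 usable case for final data analysis", and closes with "For this modification, there were no changes to the study protocol". The summary of the 2nd contract modification in part C says of the 2nd revision: "This was the final protocol in place for the remainder, and majority, of the study". Section 4a as written there was therefore still in force.

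**The concern.** To keep a required number after a proportion d is lost, that number is divided by (1 - d). Multiplying it by (1 + d) always falls short, because the loss applies to the enlarged sample. Section 4a appears to have multiplied.

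Part D then works in the right direction, from enrolment times retention to usable cases, but its end point is 211. The 220 of section 4a is not mentioned. The one derivation of 211 that the documents support is 264 x 0.80, so the product of the faulty inflation seems to have been adopted as the analysis target.

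The only power figure in the plan, .80, thus belongs to a sample that neither enrolment target delivers at its own attrition rate. Someone weighing a null or borderline result cannot tell what power the analysed sample was meant to have.

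**Working it through.** **Inputs.** From section 4a: 44 therapists, 5 patients each, 220 patients, power .80, standardized difference .50, intra-class correlation .15, alpha .05 (sidedness not stated), 20% dropout, 264 enrolled. From part D: 25% attrition, 281 enrolled, 211 usable.

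**The plan's figures reproduced**
- 44 x 5 = 220.
- 220 x 1.20 = 264, which is also 44 x 6.
- 281 x 0.75 = 210.75, so 211; in reverse, 211/0.75 = 281.3.

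**What 264 delivers at 20% dropout**
- 264 x 0.80 = 211.2 patients, and 211.2/44 = 4.8 per therapist.
- Shortfall: 220 - 211 = 9 patients, 9/220 = 4.1%.
- 264 retains 220 only if dropout is 1 - 220/264 = 16.7%.
- Rounding to whole patients per therapist does not explain it: 5/0.80 = 6.25, so 6 per therapist is still too few.

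**What keeping 220 would need**
- At 20%: 220/0.80 = 275.
- At 25%: 220/0.75 = 293.3, so 294 (294 x 0.75 = 220.5).

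**Size of the loss in power.** The Optimal Design run cannot be repeated, because the within-patient variance inputs are not given. Two approximations size the difference, both assuming two-sided alpha.

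1. Simple cluster formula with the stated inputs, n patients per therapist and 42 degrees of freedom. The noncentrality is 0.5 / sqrt[4 x (0.15 + 0.85/n) / 44].
   - n = 5 (220 patients): noncentrality 2.93, power .817.
   - n = 211/44 = 4.80: noncentrality 2.90, power .808.
   - On this formula, power reaches .80 from 203 patients.
2. Power set to exactly .80 at 220, so that the noncentrality there is 1.960 + 0.842 = 2.802 on the normal scale.
   - Information proportional to patients: 2.802 x sqrt(211/220) - 1.960 = 0.784, power .783.
   - Cluster scaling: the design effect is 1 + (5 - 1) x 0.15 = 1.60 at 220 and 1 + (4.795 - 1) x 0.15 = 1.569 at 211. The effective sizes are 220/1.60 = 137.5 and 211/1.569 = 134.5. Then 2.802 x sqrt(134.5/137.5) - 1.960 = 0.81, power .791.

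The loss is about 1 point on the first approach and 1 to 2 points on the second.

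**The case against.** The strongest reply is that the arithmetic is wrong but hardly matters. On the cluster formula with the stated inputs, 211 patients still give .808, and values below .80 appear only if power is fixed at exactly .80 at 220. That formula also treats therapists as if they were allocated to arms. Section 2a has each therapist treating patients in both conditions, so much of the therapist effect would cancel. Taking total variance 1, two-sided alpha and balance within therapist (none of which the documents give), power is about .98 at 220 and .97 at 211 with no therapist-by-condition variance. With that variance at .30 it is about .91 and .90. This point stands: none of these figures is the trial's actual power, and no breach of .80 has been shown. All of them agree that the loss is small.

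A second reply is that a growth model can use partial data from patients who drop out, so 211 may understate the information retained. That softens the shortfall but does not remove it. Part D counts only usable cases. Section 2a also removes match-arm patients with no eligible therapist from the primary analyses, and says the same oversampling covers them.

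A third reply is that 281 is correct for its stated target of 211, and that the executed modification is not reproduced in the documents. Both are true. The fault in part D is the unexplained move from 220 to 211, not its multiplication; and the absence of a power figure at 211 can be asserted only of the text available.

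**Conclusion.** The concern holds. Section 4a multiplies where it should divide, so 264 does not preserve the 220 patients it names as the minimum for .80 power. At the plan's own 20% dropout it leaves about 211. Part D then sizes 281 to that 211 at 25% attrition, leaves the protocol unchanged and gives no power for 211.

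The inflation error rests on the documents' figures alone and needs no outside assumption beyond the plan's own convention that dropouts do not count as usable cases. Its size is modest: 9 analysed patients, 4.1%, and about 1 to 2 points of power if alpha is two-sided. It is not a finding that the trial is underpowered; that cannot be decided without the variance components and the sidedness of alpha. It should be corrected because it sits in the only sample-size justification in the plan.

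**What to change.** Rerun the Optimal Design calculation at 211 analysed patients (about 4.8 per therapist with 44 therapists), stating the sidedness of alpha and the number of therapists, and report that power in place of .80 at 220. The number of therapists needs stating because 44 therapists at the quota of 6 in section 2a give 264 places, fewer than 281. Correct the dropout sentence in section 4a, and add a line to part D that explains the change from 220 to 211.

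For information, the text can state that keeping 220 would take 275 enrolled at 20% dropout or 294 at 25%.

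The cost is one rerun of an existing calculation and wording in two places. No further patients are needed if power is restated at 211.

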assessments *other than* the M.I.N.I., which was resulting in missing data regardless. We also wondered whether when people read the consent form and saw that we were asking them to engage in two 30-minute phone calls in addition to completing measures, this may have deterred them from enrolling. Thus, given the limited yield (at best) and overt disruption (at worst) of the diagnostic interview, we dropped it from our protocol. Fortunately, the data were never intended to be primary, and we could still characterize our sample with the TOP data (our primary match and outcome measure). Further, the diagnostic assessments were not included in PsycBC's standard intake process (as they were with our former clinical partner). Thus, using them actually rendered our study less naturalistic vis-à-vis the system that we were trying to affect/improve with our intervention.

- PsycBC hired a full-time employee whose sole job description was to recruit patients to the trial.
- Our PsycBC collaborator, [name], who holds a significant amount of regional credibility, agreed to liaise with community physicians to market the study, which they could then mention to their patients prior to them contacting PsycBC. We suspected that the more patients were in the know about the project prior to calling or arriving for care, the more likely they would agree to take part vs. view it as an unexpected inconvenience.
- We posted a special announcement about the study on PsycBC's website, with the idea that it might predispose patients to participate if they read about the potential personal benefits before the intake call.
- We raised the upper age limit of study-eligible patients to 70 instead of 65. The literature does not demarcate older adulthood at 65, so we felt that raising the age would have no untoward effect on response to treatment.
- We continued to monitor PsycBC therapists who were not enrolled in the study, but now had the requisite number of baseline cases with TOP data for which we could establish a baseline report card. This would allow us to recruit from this pool if there was employment turnover from study-enrolled clinicians, or if other strategic needs arose (e.g., if having more therapists at a particular site could also positively affect patient recruitment and retention).
- The project's milestone schedule was unrevised for this contract modification.

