After the full baseline assessment, patients will be randomly assigned to condition (scientifically informed matched vs. pragmatic match) with a participating PsycBC provider. The UMass PC will generate the randomization sequences using an online random generator. Within condition, patients will be assigned sequentially to the therapists until they reach their study quota of 6 patients. Patients in the match condition will be assigned to therapists who have a demonstrated strength (derived from the baseline period) in treating, at a minimum, the patient's highest self-reported distress domain on the TOP-CS. Beyond the minimal match on the most elevated TOP-CS domain, our match algorithm will attempt to match patients to therapists on as many TOP-CS dimensions as possible, ultimately providing PsycBC with at least several well-matched choices for assignment within the match condition. In order to preserve this level of choice, there will be natural variability in the number of well-matched domains (some patients matched only on the minimum 1 TOP-CS domain, others matched on 2 or more domains). The match variability across both conditions will allow us to measure degree of match dimensionally as a moderator variable of our main treatment effect. Therapists will also be unaware of their patient's treatment condition (double blind), and they will treat both matched and non-matched patients (i.e., they will be crossed over the two conditions to minimize administrative disruptions). In the low probability event that there is no therapist meeting minimal match criteria for a patient in the match condition, that patient will be removed from the primary study analyses (though will, of course, still be offered treatment-as-usual at the clinic) and replaced with the next patient where a match does exist. As described in our power analysis below, we are oversampling in order to account for these "dropouts," or removed data points.

In addition to the baseline assessments already described, patients will be assessed via online surveys at regular intervals during treatment (the secure ORI platform will email hyperlinks to these surveys with reminders to complete them at the appropriate time intervals; the UMass PC can also follow-up with phone calls if needed). These during-treatment assessments will include the TOP-CS and measures

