Finally, note that in the event that a participant (either a patient or therapist) withdraws from the study during phase 2, the other dyad member (either the patients seen by a withdrawing therapist or the therapist treating a withdrawing patient) will not be penalized; that is, as long as they have already consented to the study, they will receive the full amount of reimbursement (i.e., a \$50 gift card) regardless of the point at which their patient/therapist withdraws. However, note that consistent with the wishes of the participant, we will, of course, stop collecting data at the point of withdrawal (i.e., if therapists withdraw, we will stop collecting data from their patients who will be compensated fully; if patients withdraw, we will stop collecting data from their therapist regarding that patient and the therapist will be compensated fully for that patient).

- i. **Please state: A: The total expected duration of the study, including the time expected for data analysis (e.g., This study is expected to last 1 year) AND B: How much time each subject is expected to be involved in the study (e.g., The involvement of each subject will be 1-session for a total of 90 minutes).**
A) The project is funded in the form a cost-reimbursement contract for which a specific milestone schedule exists. The contract start date is 9/15/16 and the contract term date is 6/15/20. All analyses will be completed by the term date. Details are available in the attached updated milestone schedule.

B) Therapist subjects will be involved for 2 months in phase 1, as well as through the phase 2 trial (approximately 2 years, though with variability depending on when they have been assigned and have treated their 6 study cases). Patients in phase 2 only will be involved in the study protocol through their actual termination point or 16 weeks, whichever comes sooner (we will also conduct a follow-up outcome assessment at 1 year after termination on a randomly-selected subsample of 40 patients).

5. Risks

HHS Regulations define a subject at risk as follows: "...any individual who may be exposed to the possibility of injury, including physical, psychological, or social injury, as a consequence of participation as a subject in any research..." This also includes risks to subject confidentiality and any discomforts, hazards, or inconveniences.

For the categories below, include a description of risks.

a. **Describe the risks related to:**

Physical well-being

None anticipated.

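### When a therapist withdraws, outcome collection stops for up to six randomised patients who have consented and not withdrawn, which truncates their follow-up

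*Combined protocol and SAP*

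**What the plan says.** The rule stands in Part C of the combined document (2nd revision), section 4, item h, Compensation, in the closing paragraph on withdrawal. Collection is to "stop collecting data at the point of withdrawal", and the paragraph spells this out: "if therapists withdraw, we will stop collecting data from their patients who will be compensated fully". The reason given is respect for the wishes of the participant who withdraws. The same paragraph separates that participant from the affected patients: "the other dyad member (either the patients seen by a withdrawing therapist or the therapist treating a withdrawing patient) will not be penalized".

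The rule is current. It appears in all three versions of the protocol. The introduction to Part C says that the 2nd revision stayed in place to the end of the study, and Part D reports no later protocol change. No other section lets these patients' outcome collection continue.

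Three other provisions bear on it, all in Part C:

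- Section 2.a, on patient surveys: "the secure ORI platform will email hyperlinks to these surveys". Patients complete them on tablets or home computers.
- Section 2.a, on caseload: "patients will be assigned sequentially to the therapists until they reach their study quota of 6 patients".
- Section 4.a, on sample size: 44 therapists and 220 patients for power .80, raised to 264 for 20% dropout at the patient level.

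**The concern.** The withdrawing participant is the therapist, but the follow-up that ends is the patient's. The patient's TOP-CS, SCL-10, EIS and IIP-32 are self-reports that need nothing from the therapist. Treatment is naturalistic in both arms, and nothing says that a therapist who leaves the study stops treating the patient. The rule can therefore end follow-up of a patient who is willing, paid in full and still in the assigned dyad.

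At stake is avoidable missing primary-outcome data after randomisation. The primary analysis compares linear change rates, and these depend heavily on late measurements. The loss falls on all of one therapist's current patients together, and the sample size makes no allowance for therapist withdrawal. Balance by arm is not assured either: match-arm patients go only to therapists strong in their most elevated domain, so a therapist's caseload need not split evenly.

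**Working it through.** **1. Ceiling per withdrawal.** The quota is 6, and 44 × 6 = 264. One therapist is at most 6/264 = 2.3% of patients, or 6/281 = 2.1% of the enrolment target in Part D.

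**2. What truncation does to one patient.** TOP-CS is taken at baseline, at odd weeks and at posttreatment. For a full course these are weeks 0, 1, 3, 5, 7, 9, 11, 13, 15 and 16: ten points, mean 8, sum of squared deviations 296. Cut off at week 8, the patient has weeks 0, 1, 3, 5 and 7: five points, mean 3.2, sum of squared deviations 84 − 5 × 3.2² = 32.8. That is one point short of the minimum of six in section 4.a. The spread in time that fixes the measurement-error part of the slope's precision falls to 32.8/296 = 11%. The patient still contributes, but weakly.

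**3. Reproducing the stated power.** Inputs from section 4.a: "standardized difference between change rates = .50", and "assuming 5 patients per therapist, an intra-class correlation of .15, and an alpha of .05". I assume a two-sided test and use a two-level approximation with therapists as clusters, because the within-patient variance terms of the cited formula are not given:

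variance = 4 × (ICC + (1 − ICC)/m)/J, non-central t with J − 2 df.

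With J = 44 and m = 5: 4 × (0.15 + 0.85/5)/44 = 0.0291, standard error 0.171, 0.50/0.171 = 2.93, power .817. The plan states .80; J = 42 gives .798. The stated figure is reproduced closely enough.

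**4. Worst case for k withdrawals.** Assume that every patient of k therapists contributes nothing and that 20% attrition applies to the rest. Then m = 6 × 0.80 = 4.8 and J = 44 − k.

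| k | Usable patients | Power |
|---|---|---|
| 0 | 211 | .809 |
| 1 | 206 | .799 |
| 2 | 202 | .789 |
| 4 | 192 | .769 |
| 8 | 173 | .722 |

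For k = 4: 40 × 4.8 = 192; variance 4 × (0.15 + 0.85/4.8)/40 = 0.0327. With 281 enrolled and 25% attrition, power goes from .808 at k = 0 to .768 at k = 4.

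**5. Sensitivity to the design.** Therapists in this trial treat patients in both arms. Taking 0.15 as the variance of the treatment effect between therapists, variance = (0.15 + 4/m)/J with J − 1 df. Power is then .905 at k = 0 and .875 at k = 4. The level is higher, and the fall is again 3 to 4 points.

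**6. How many patients are likely to be in follow-up at once.** A therapist's six cases accrue over about 2 years, and each is followed for at most 16 weeks. With even accrual (assumed), 6 × 16/104 = 0.9 patients are in follow-up at any moment. If all six accrued within 26 weeks (assumed), it would be 6 × 16/26 = 3.7. Four withdrawals would then truncate about 4 to 15 patients, against a ceiling of 24.

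**The case against.** Several points on the other side stand.

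- **Nothing is said to be discarded.** A reader might infer that the affected patients are deleted or left out of the analysis. The text stops only later collection, and a model of linear change can use the earlier scores. Patients past termination or week 16 lose at most a place in the 1-year subsample of 40.
- **Six is a ceiling.** It needs all six patients to be in follow-up together, which step 6 shows is unlikely.
- **A larger power loss is not supported.** A reader might subtract 4 × 6 = 24 from 211, reach 187, and scale power to about .73. That takes enrolled patients from a total already net of attrition and ignores clustering. The worst case is 192 and about .77.
- **Turnover is not withdrawal.** The summary of the 2nd contract modification foresees that the team could "recruit from this pool if there was employment turnover from study-enrolled clinicians". This concerns clinicians leaving the practice, and describes replacements for them. It gives no rate of study withdrawal.
- **Arm imbalance is possible but undocumented.** Therapists see patients in both conditions, so one withdrawal can affect both arms.

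The strongest objection is that the therapist is also a research subject. Patients' TOP scores measure therapist performance and are linked to the therapist by code, and the protocol recognises an employment risk from such data. Continued collection arguably continues data about someone who has withdrawn. The public document does not include the consent forms, so what therapists were promised cannot be checked. This interest is real, but it does not require ending the patient's own follow-up. It can be met by stopping the therapist's forms and ratings of the therapist, and by keeping outcomes under code.

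**Conclusion.** The concern holds as avoidable truncation of follow-up, clustered by therapist and outside the patient-level dropout allowance. The size is modest: at most 2.3% of 264 patients per withdrawal and, for four withdrawals, a fall in power from about .81 to about .77. That fall rests on an assumed number of withdrawals, on affected patients contributing nothing, and on a two-level approximation to the plan's formula. The real effect is likely to be smaller, because finished patients lose almost nothing and truncated patients keep their earlier scores. The documents do not support a reading that randomised patients are removed from the analysis, or that one arm is known to lose more than the other. The change is worth making because the loss is avoidable and the remedy is cheap.

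**What to change.** Replace the rule in section 4.h with wording such as:

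> If a therapist withdraws from the study, forms completed by the therapist stop and, on request, so do patient ratings of that therapist. Patients who have not withdrawn continue their own outcome surveys (TOP-CS, SCL-10, EIS, IIP-32) to termination or week 16, and are analysed in the arm assigned under the coded therapist identifier.

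The amendment should list which forms count as ratings of the therapist. It should also be reconciled with the rule in sections 2.a and 4.g that treats a patient's request for transfer as a dropout point, so that it is clear which rule applies when a therapist's withdrawal also leads to a change of therapist.

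Cost: an amendment to the protocol and to both the patient and therapist consent forms, IRB approval, and a few more reminders. The surveys are already sent by the platform and these patients are already paid in full. Patients who prefer to stop can still withdraw themselves.
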